 Dapagliflozin therapy in TAVI patients with prior history of HF and diabetes mellitus, reduced LVEF (LVEF ≤ 40%) or renal dysfunction (eGFR 25-75 ml/min/1.73 m2), is associated with reduced 1-year mortality or worsening of HF.

Secondary hypotheses:

- 1) Dapagliflozin therapy in TAVI patients with prior history of HF and diabetes mellitus, reduced LVEF (LVEF ≤ 40%) or renal dysfunction (eGFR 25-75 ml/min/1.73 m2), is associated with reduced 1-year CV mortality
- 2) Dapagliflozin therapy in TAVI patients with prior history of HF and diabetes mellitus, reduced LVEF (LVEF ≤ 40%) or renal dysfunction (eGFR 25-75 ml/min/1.73 m2), is associated with reduced 1-year incidence of AF.
- 3) Dapagliflozin therapy in TAVI patients with prior history of HF and diabetes mellitus, reduced LVEF (LVEF ≤ 40%) or renal dysfunction (eGFR 25-75 ml/min/1.73 m2), is associated with improvement in functional class.

STUDY DESIGN AND ENDPOINTS

DESCRIPTION OF THE STUDY DESIGN

Dapa-TAVI is a pragmatic, controlled, prospective, randomized, open-label blinded endpoint (PROBE design) clinical trial. Patients being discharged after TAVI who meet all inclusion criteria, and none of the exclusion criteria, will be eligible for the enrollment. Patients will be 1:1 randomized to 1 of these 2 arms:

- **Intervention group:** Sodium-glucose cotransporter-2 (SGLT-2) inhibitor therapy with daily oral dose of dapagliflozin 10 mg.
- **Control group:** no SGLT-2 inhibitor therapy with dapagliflozin.

Apart from dapagliflozin therapy (or control), patients will be treated according to current standards (per managing physician prescription).

STUDY ENDPOINTS

> PRIMARY ENDPOINT

• Incidence rate of the composite of all-cause mortality or worsening HF (including hospitalization for HF or an urgent visit resulting in intravenous therapy for HF).

> SECONDARY ENDPOINTS

- Indicence rate of individual components of primary endpoint.
- Incidence rate of CV death.
- Incidence rate of atrial fibrillation (AF).

> TERTIARY ENDPOINTS

- Improvement in NYHA class.
- Safety endpoints:
 - Symptomatic hypotension. Symptomatic hypotension includes postural dizziness with systolic blood pressure < 100 mmHg, and orthostatic hypotension (defined as a decrease of >20 mmHg in systolic blood

- pressure or >10 mmHg in diastolic blood pressure from a supine to a standing position).

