- 6. Death due to CV Haemorrhage: refers to death related to haemorrhage such as a non-stroke intracranial haemorrhage, non-procedural or non-traumatic vascular rupture (e.g., aortic aneurysm), or haemorrhage causing cardiac tamponade.
- 7. Death due to Other CV Causes: refers to a CV death not included in the above categories but with a specific, known cause (e.g., pulmonary embolism or peripheral arteria disease).
- **Non-CV Death:** Non-CV death is defined as any death not covered by CV death and falling into one of the following categories:
 - 1. Pulmonary failure
 - 2. Renal
 - 3. Gastrointestinal causes
 - 4. Hepatobiliary
 - 5. Pancreatic
 - 6. Infection (includes sepsis)
 - 7. Inflammatory (e.g., Systemic Inflammatory Response Syndrome / Immune (including autoimmune, may include anaphylaxis from environmental (e.g., food allergies)
 - 8. Haemorrhage that is neither CV bleeding or stroke
 - 9. Non-CV procedure or surgery
 - 10. Trauma
 - 11. Suicide
 - 12. Non-prescription drug reaction or overdose

- 13. Prescription drug reaction or overdose
- 14. Neurological (non-cardiovascular)
- 15. Malignancy
- 16. Other, please specify.
- Undetermined Cause of Death: Undetermined Cause of Death refers to a death not attributable to one of the above categories of CV death or to a non-CV cause. Inability to classify the cause of death may be due to lack of information (e.g., the only available information is "patient died") or when there is insufficient supporting information or detail to assign the cause of death. In general, most deaths should be classifiable as CV or non-CV, and the use of this category of death, therefore, should be discouraged and should apply to few patients in well-run clinical trials.
- Atrial fibrillation (AF): The diagnosis of AF is based on the physical finding of an irregular supraventricular heart rhythm and is confirmed with an ECG or rhythm strip.
- Functional status: Functional status will be measured as New York Heart Association (NYHA) functional classification of heart failure for dyspnea.

EVENT ADJUDICATION

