Randomization introduces a deliberate element of chance into the assignment of treatments to subjects in a clinical trial. In this trial, randomization procedure is organized centrally, and it is characterized by being stratified by center and follows a permuted-block design with varying block sizes to reduce predictability of the random sequence.

Blinding:

As this trial follows a PROBE design, open-label and blinded endpoint adjudication are intrinsic characteristics. Masking is no implemented for patient and care provider. Therefore, to reduce potential bias, the endpoint adjudication panel remains blinded to treatment allocation and hard clinical meaningful endpoints have been selected as primary endpoint.

• Multiplicity:

Multiplicity can raise concerns regarding type I error. To address multiplicity problems, two strategies are implemented. First, a composite endpoint is selected as primary endpoint. Second, Haybittle-Peto approach is applied to account for interim analyses.

• External validity:

The pragmatic design of this trial, as evaluated through PRECIS-2 guidelines, increases the generalizability of its conclusions to real daily clinical practice.

DESCRIPTIVE ANALYSIS

The distribution of continuous variables will be analyzed with graphical methods. For normally distributed variables, results will be expressed as mean \pm SD; otherwise they will be represented as median (first quartile to third quartile). Categorical variables will be expressed as absolute frequency (%). Significance testing of baseline differences between treatment groups will be not performed.

PRIMARY ANALYSIS

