Primary analyses will be performed in the "full data set" in an intention-to-treat fashion. The intervention arm will be compared against the control arm for the composite primary endpoint. Time-to-event will be evaluated using the Kaplan-Meier survival analysis followed by multivariable Cox proportional hazards model. Hazard ratios (HR) with corresponding 95% confidence intervals will be calculated for treatment effect estimation. All patients without an event will be censored at last day of follow-up. Patients that withdraw from follow-up will be considered censored on the day of withdrawal. Due to the randomization process and the large sample size of the trial, it will be not expected the presence of covariate relevant imbalances between treatment groups. However, for exploratory purpose, standardized differences will be calculated. Those known prognostic factor presenting an imbalance higher than 0.1 standardized difference will be included in the multivariable Cox model. For all tests, we will use 2-sided p-values with alpha ≤0.05 level of significance.

SECONDARY ANALYSIS

The secondary endpoints will be the individual components of the primary composite endpoint, besides CV mortality and the development of new atrial fibrillation. Analyses will be performed following the same guidelines described for primary analysis. Multiplicity adjustment will be not implemented because the hierarchical structure between primary and secondary endponits.

To better explore the treatment effect under ideal circumstances (explanatory approach), primary and secondary endpoint analyses will be replicated in the "per protocol data set" using same methods described above.

SUBGROUP ANALYSIS

All subgroup analyses will be performed using interaction models based on the primary analysis model, also including the subgroup in question and the treatment-subgroup interaction as factors, and presented as treatment hazard ratios for each subgroup and the interaction p-value. Subgroups will be specified in the endpoints section below.

PRE-SPECIFIED SUB-GROUP ANALYSES

- > Diabetic vs non-diabetic patients.
- ightharpoonup LVEF < vs > 40%.
- \geq 80 years vs < 80 years of age on recruitment
- ➤ Males vs females
- ➤ Atrial fibrillation versus sinus rhythm
- > Hypertensive vs normotensive patients
- ➤ Moderate-severe vs mild LVH.
- > Treatment with beta-blockers vs. no beta-blockers

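### Worsening HF, CV death and new AF inherit the Kaplan-Meier plan with no competing-death estimate, a small reporting error, and the stated hierarchy does not control error among the secondary endpoints

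*Combined protocol and SAP*

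**What the plan says.** All references are to the combined protocol and SAP.

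- **Method.** Primary Analysis plans Kaplan-Meier followed by a Cox model, with the HR as the effect estimate. On censoring: "All patients without an event will be censored at last day of follow-up".
- **Inheritance.** Secondary Analysis lists the components of the composite, CV mortality and new AF, and adds: "Analyses will be performed following the same guidelines described for primary analysis". No section plans a cumulative incidence function or names death as a competing event.
- **Target.** Two secondary hypotheses (Hypotheses section) are worded as one-year outcomes: dapagliflozin "is associated with reduced 1-year CV mortality" and "is associated with reduced 1-year incidence of AF".
- **Undetermined deaths.** The event definitions describe these as deaths "not attributable to one of the above categories of CV death or to a non-CV cause".
- **Multiplicity.** Secondary Analysis: "Multiplicity adjustment will be not implemented because the hierarchical structure between primary and secondary endponits". Primary Analysis: "For all tests, we will use 2-sided p-values", at a 0.05 level. Reducing Bias: "To address multiplicity problems, two strategies are implemented". Those two are the choice of a composite primary endpoint and the Haybittle-Peto rule for interim looks.

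**The concern.** There are two separate matters.

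**Competing death.** A patient who dies of another cause can no longer have a first HF event, a CV death or new AF. Censoring such patients is correct for a cause-specific HR. It is not correct for the proportion who have the event within a year, because Kaplan-Meier then treats the dead as still able to have it. The only curve planned therefore does not estimate the one-year quantities that the hypotheses name. All-cause death has no competing event, so it is unaffected.

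**Multiplicity.** The reason given for not adjusting is the ranking of primary above secondary endpoints. No rule says that the secondary tests wait for a significant primary, and no order is set among them. The two strategies in Reducing Bias deal with the primary endpoint and the interim looks. The plan therefore leaves open whether p<0.05 on CV death or AF would be a formal claim or a description.

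**Working it through.** **The plan's own figure.** With HR 0.70, two-sided 0.05 and power 0.80, the Schoenfeld formula gives 4(1.960+0.842)²/(ln 0.70)² = 247 events. Then 247/0.255 = 969, and 969/0.95 = 1,020. The stated sample size reproduces, and neither matter below touches it.

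**Worsening HF.** Inputs: 30% control composite (Sample Size); one-year mortality of about 10% (Protocol Synopsis; Possible benefit of Dapagliflozin in TAVI patients) or 10 to 20% (Clinical outcomes after TAVI). Let s be the share of composite events in which HF comes first.

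- At 10% mortality, at most 10 of the 30 points are death without prior HF, so s is at least 20/30 = 67%. At 20% mortality, s is at least 10/30 = 33%.
- The rationale also says that almost one in three patients with prior HF admission are readmitted for HF within a year. Against a 30% composite this pushes s towards 100%.

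With constant cause-specific hazards, the true incidence is 0.30 × s and one minus Kaplan-Meier is 1 − 0.70^s.

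| s | True incidence, % | 1 − KM, % | Excess, points |
|---|---|---|---|
| 33% | 10.0 | 11.2 | 1.2 |
| 50% | 15.0 | 16.3 | 1.3 (about the maximum) |
| 67% | 20.0 | 21.2 | 1.2 |
| 75% | 22.5 | 23.5 | 1.0 |
| 90% | 27.0 | 27.5 | 0.5 |
| 100% | 30.0 | 30.0 | 0 |

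The excess partly cancels between arms. With HR 0.70 on HF and s of 67 to 75%, the arm difference is 0.25 to 0.56 points too large, depending on whether death also falls. At s = 50% with HR 0.70 on both, the treated arm has true incidence 0.5 × (1 − 0.70^0.70) = 11.05% and 1 − 0.70^0.35 = 11.74%. The difference reads as 16.33 − 11.74 = 4.60 instead of 15.00 − 11.05 = 3.95, so 0.65 too large. For comparison, with 510 per arm and s of 67 to 75%, the 95% CI half-width is 3.5 to 3.6 points for control incidence and 4.6 to 4.9 for the difference.

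**CV death.** With mortality m and CV share c (50 to 70%, assumed), the excess is 1 − (1 − m)^c − m × c. At m = 10% it is 0.13 and 0.11 points; at m = 20% it is 0.56 and 0.46.

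**New AF.** With AF incidence a (5 to 15%, assumed) and death without AF d (10 to 20%), the excess is 1 − (1 − a − d)^(a/(a+d)) − a. For a = 5% it is 0.27 (d = 10%) and 0.59 (d = 20%); for a = 15% it is 0.85 and 1.86.

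**Multiplicity.** Suppose dapagliflozin reduces HF only, so that death, CV death and AF are all null. CV deaths are a subset of deaths, so their test statistics correlate at about √c: 0.71 for c = 0.5 and 0.84 for c = 0.7. The bivariate normal probability that neither is significant is 0.9169 and 0.9244. With AF independent:

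- c = 0.5: 1 − 0.9169 × 0.95 = 12.9%.
- c = 0.7: 1 − 0.9244 × 0.95 = 12.2%.
- Correlation from 0.5 to 0.9: 13.6% down to 11.7%.
- CV death and AF alone, independent: 1 − 0.95² = 9.8%.

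A patient-level simulation adds an explicit primary gate (20,000 trials per scenario, 510 per arm, 5% withdrawal, no interim looks; 10% new AF and 35% baseline AF assumed; s of 67 to 75%). At HF HR 0.70 the error is 11.8 to 13.1% given a significant primary. Counted over all trials it is 5.3 to 6.9%, because the primary is significant in only 45 to 55%. At HF HR 0.55 the primary is significant in 81 to 82% and the error over all trials is 9.2 to 9.6%. If every endpoint is null, the gate holds it to about 3.6%. These simulated figures have not been independently repeated.

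**The case against.** **On competing death.** The plan never says that one minus Kaplan-Meier will be reported as one-year incidence. It names the HR as the effect estimate and calls the endpoints incidence rates. With a year of follow-up for everyone and 5% withdrawal, a crude percentage would be close to the cumulative incidence. The hypotheses are directional, and the Cox test does not change. All of this stands. A reader might infer that the secondary Cox analyses are invalid or that a biased incidence is certain to be published; the documents support neither. What remains is that the only planned curve does not match the one-year wording.

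A reader might also infer that the definitions place undetermined deaths with the competing deaths. They do not: the label excludes CV and non-CV causes alike and sets no analysis rule.

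**On multiplicity.** The lack of adjustment is openly disclosed, and no section claims error control among the secondary endpoints. The 12 to 14% needs HF to improve while CV death is exactly null. That is a strong assumption, because deaths from HF count as CV deaths. Read as a gate, the sentence gives 5 to 7% over all trials at HF HR 0.70, close to nominal. These points limit the size, but the stated reason still does not provide control once a real HF effect opens the gate.

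**Conclusion.** Both matters hold, in modest form, and the plan should be reworded.

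**Competing death.** One minus Kaplan-Meier read as one-year incidence is too high by about 0 to 1.3 points for worsening HF within the 30% composite, 0.1 to 0.6 for CV death and 0.3 to 1.9 for new AF. Constant hazards, the CV share and the AF incidence are assumptions. For worsening HF the error is well inside sampling error. No conclusion is expected to turn on this part.

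**Multiplicity.** This is the weightier part. A primary-to-secondary ranking protects the secondary endpoints only while the composite null is true. If only HF improves, the error among death, CV death and AF is about 12 to 14% once the primary is significant. The 5 to 7% over all trials applies to a gate at HF HR 0.70 with s of 67 to 75%, and it rises with the chance of a significant primary.

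Two stronger readings fail. Error of 16 to 19% for four tests applies only if all four are null and no gate operates. The 45 to 55% primary success is not a criticism of power: it comes from assuming an effect on HF alone, whereas the plan assumes HR 0.70 on the whole composite.

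**What to change.** Wording only, in Secondary Analysis:

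1. Report worsening HF, CV death and new AF as cumulative incidence functions with other deaths as the competing event, and label the Cox result a cause-specific HR. Take patients without baseline AF as the risk set for new AF; the section already says new, and baseline AF is among the variables collected. State how undetermined deaths are handled for CV death, with the alternative as a sensitivity analysis.
2. Replace the hierarchy sentence with a statement that secondary p-values are unadjusted and descriptive. If the sponsor wants formal secondary claims, write instead a fixed testing order, opened only by a significant primary result.

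No new data are needed, and the primary analysis and sample size stay as they are. The cost is that some secondary endpoints lose a formal claim.
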